APPENDIX 10. AESI – SLOWING OF VENTRICULAR REPOLARIZATION

Preferred Term
Electrocardiogram QT interval abnormal
Electrocardiogram QT prolonged
Long QT syndrome
Long QT syndrome congenital
Torsade de pointes
Ventricular tachycardia

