 13. Have initiated or had dose adjustment to hormone replacement therapy (including testosterone) or an oral contraceptive within 30 days of screening
 14. Have used inducers or moderate to strong inhibitors of cytochrome P450 (CYP) 3A4 (prescription medications, over-the-counter medications [OTC], or dietary supplements) within 30 days prior to screening (see [Appendix A](#) for examples of prohibited CYP3A4 modulators)
 15. Have received electroconvulsive therapy treatment within the last 2 years, or received more than 1 course of electroconvulsive treatment during their lifetime
 16. Pose a current suicide risk, as evidenced by any of the following:
 - a. it is the opinion of the investigator that the subject may be at risk for suicide
 - b. the subject responds “Yes” to Question # 4 (“Active Suicidal Ideation with Some Intent to Act, Without Specific Plan”) or Question # 5 (“Active Suicidal Ideation with Specific Plan and Intent”) on the Baseline Columbia Suicide Severity Rating Scale (C-SSRS), if the most recent episode occurred within the past 12 months
 - c. the subject has attempted suicide within the past 2 years

17. Have a QT interval >450 msec for men and >470 msec for women, assessed in a relaxed state, as corrected by the Fridericia formula (QTcF) observed at Visit 1 or Visit 2
 18. Have an aspartate aminotransferase or alanine transaminase measurement of >2 times the upper limit of normal at Visit 1.
 19. Have current evidence of or history of any of the following:
 - a. compromised respiratory function (eg, chronic obstructive pulmonary disease, respiratory depression, signs or symptoms of hypoxia at screening)
 - b. thyroid pathology (unless stabilized and euthyroid for >3 months at the time of screening)
 - c. seizure disorder (excluding febrile seizures)
 - d. hepatitis or human immunodeficiency virus (HIV) infection
 - e. myasthenia gravis
 - f. any contraindicated medical condition as per the approved labeling for buprenorphine
 20. Have current evidence of, or a history in the past 12 months of, alcohol or substance abuse or dependence (excluding nicotine) per DSM-IV-TR criteria as assessed by the MINI
 21. Have a positive breath alcohol test at screening
 22. Have a history of intolerance, allergy or hypersensitivity to BUP or opioid antagonists (eg, naltrexone, naloxone)

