3.7.3. Adverse Events of Special Interest

Adverse events of special interest (AESIs) will be summarized by Preferred Term and by prior ALKS 5461 exposure and overall during treatment period for the Safety Population / Post-discontinuation Safety Population for any TEAEs or PDEAEs of special interest. The following summaries will be created for AESI:

- TEAEs associated with abuse potential
- TEAEs associated with dependence
- PDEAEs associated with withdrawal
- TEAEs associated with suicidal ideation and behavior
- TEAEs associated with hypomania / mania
- TEAEs associated with central nervous system (CNS) depression and sedation
- TEAEs associated with respiratory depression
- TEAEs associated with orthostasis / hypotension
- TEAEs associated with hypersensitivity

- TEAEs associated with slowing of ventricular repolarization
- TEAEs associated with hepatic effects
- TEAEs associated with sexual dysfunction

TEAEs associated with abuse potential will be presented by Adhoc System Organ Class and Preferred Term, where Adhoc System Organ Class is manually classified by Alkermes medical director as 3 categories: abuse behavior, euphoria related, and non-specific.

TEAEs associated with dependence will be presented for subjects with any exposure, ≥4 weeks exposure, and <4 weeks exposure, respectively.

PDEAEs associated with withdrawal will be presented for subjects with any exposure, ≥4 weeks exposure, and <4 weeks exposure, respectively. AESIs associated with withdrawal are PDEAEs that occur from >2 to 16 days post last dose as this is the period during which physiological opioid withdrawal presents by considering half-lives of both BUP and SAM.

Supportive AE listings will be provided for each special interest group. Narratives will be provided for clinically meaningful events within each AESI group.

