APPENDIX 4. AESI – SUICIDAL IDEATION AND BEHAVIOR

Preferred Term
Depression suicidal
Suicidal ideation
Suicide threat
Suicidal behavior
Suicide attempt
Intentional overdose
Multiple drug overdose
Multiple drug overdose intentional
Overdose
Poisoning deliberate
Completed suicide
Intentional self-injury
Self injurious behavior
Self mutilation
Self-injurious ideation
Columbia suicide severity rating scale abnormal

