APPENDIX 7. AESI – RESPIRATORY DEPRESSION

Preferred Term
Acute respiratory failure
Apnoea
Apnoeic attack
Bradypnoea
Breath holding
Breath sounds abnormal
Breath sounds absent
Central-alveolar hypoventilation
Hypopnoea
Hypoventilation
Hypoventilation neonatal
Infantile apnoea
Lung hypoinflation
Neonatal respiratory arrest
Neonatal respiratory depression
Neonatal respiratory failure
Postoperative respiratory failure
Respiratory arrest
Respiratory depression
Respiratory depth decreased
Respiratory failure
Respiratory paralysis
Respiratory rate decreased

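### The ventricular-repolarization AESI list includes two ventricular arrhythmias but omits ventricular fibrillation, cardiac arrest and sudden death, so events coded to those terms are left out of this AESI's table, listing and narratives

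*SAP*

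**What the plan says.** SAP Section 3.7.3 sets the rule for all AESI outputs: "Adverse events of special interest (AESIs) will be summarized by Preferred Term and by prior ALKS 5461 exposure and overall during treatment period". One of its twelve categories is "TEAEs associated with slowing of ventricular repolarization". The section also promises a supportive listing for each category, and narratives for clinically meaningful events that fall within a category.

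Appendix 10 supplies the terms for this category. There are six: "Electrocardiogram QT interval abnormal", "Electrocardiogram QT prolonged", Long QT syndrome, Long QT syndrome congenital, Torsade de pointes and "Ventricular tachycardia". Neither Section 3.7.3 nor the appendix says how they were chosen.

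QT also receives attention elsewhere. Protocol Section 7.2.2 excludes New Subjects who "Have a QT interval >450 msec for men and >470 msec for women", using Fridericia's correction. SAP Section 3.7.6 analyses QTcF directly, with limits of 450, 480 and 500 msec and changes of more than 30 and more than 60 msec.

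**The concern.** An AESI table exists so that a reader looking for one kind of harm finds the relevant cases assembled in one place. Since it is built by Preferred Term, the list decides what is assembled. Appendix 10 already mixes ECG findings with clinical arrhythmias, and Ventricular tachycardia is not specific to QT prolongation. Having gone that far, it leaves out ventricular fibrillation, cardiac arrest and sudden death.

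What is at stake is how the output reads. A zero in the repolarization table could be taken to mean that no serious ventricular event occurred, when such an event had been coded to a term outside the list. The listing would not show that subject either, and the event would not come up for a narrative under this category.

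**Working it through.** No power, alpha or sample-size figure is involved, and the plan states no number to reproduce. The check compares term lists and then traces an event through the planned outputs.

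**Step 1: what the list holds.** 4 QT or long-QT terms + 2 ventricular arrhythmias = 6 terms. Terms for ventricular fibrillation, cardiac arrest or sudden death: 0. The list is alphabetical, and all three would sort before its last entry (cardiac arrest before the first term, sudden death before Torsade de pointes, ventricular fibrillation before Ventricular tachycardia). The absence is therefore not text lost at the end of the page.

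**Step 2: whether another AESI list picks them up.** None of Appendices 1 to 9, 11 or 12 contains any of the three. The nearest entries are Circulatory collapse and Shock (Appendices 8 and 9), Syncope (Appendices 3 and 8) and Loss of consciousness (Appendix 6). All are different Preferred Terms.

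**Step 3: how far the other lists go.** Appendix 7 reaches "respiratory arrest", Appendix 4 reaches "Completed suicide", and Appendix 11 reaches Acute hepatic failure and Liver transplant. Each extends to the terminal outcome of its own process.

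**Step 4: follow an on-treatment event through the SAP outputs.**

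| Output | Coded to Ventricular tachycardia | Coded to ventricular fibrillation, cardiac arrest or sudden death |
|---|---|---|
| By-subject AE listing (3.7.2) | Included | Included |
| TEAEs by System Organ Class and Preferred Term (3.7.2) | Included | Included |
| SAE tables, fatal and non-fatal (3.7.2) | Included if serious | Included if serious |
| Deaths (3.7.2) | Included if fatal | Included if fatal |
| QTcF limits and changes (3.7.6) | Depends on tracings, not coding | Depends on tracings, not coding |
| Repolarization AESI table (3.7.3) | Included | **Not included** |
| Repolarization AESI listing (3.7.3) | Included | **Not included** |
| Narrative pool for this AESI (3.7.3) | Included | **Not included** |

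The two columns differ only in the last three rows. On narratives, the SAP's other commitments concern C-SSRS suicidal behavior and completed suicide (3.7.7) and COWS shifts (3.7.8). It makes no general commitment to a narrative for every SAE, although a document outside the two reviewed here may do so.

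**Step 5: whether the SAP has a model for a broader tier.** It does. Section 3.7.3 and Appendix 1 divide abuse-potential terms into three classes, one of them non-specific. Terms are also placed in more than one list: Syncope in Appendices 3 and 8, Somnolence in 1 and 6, Overdose in 1 and 4.

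**The case against.** The strongest reply is that the list is deliberately specific to a mechanism. Cardiac arrest and sudden death have many causes, and nothing in the documents says that they belong under slowed repolarization. The comparators in other appendices each name the process of their own list, and the equivalent here is Torsade de pointes, which is present. No AESI appendix lists cardiac arrest or sudden death, so Appendix 10 is not unusual on those terms. The events are not lost, because Section 3.7.2 tabulates them elsewhere, and QTcF is analysed directly with unscheduled tracings included in the outlier analysis.

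Much of this stands. Scope is a judgement that the documents do not settle, and safety capture is complete at the level of the general AE tables. The specificity argument weakens, though, because Ventricular tachycardia is already on the list and other appendices admit very general terms, such as Dizziness and Shock in Appendix 8 and Headache and Nausea in Appendix 3. A separate tier meets the remaining objection, since the narrow count is unchanged.

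Three stronger readings may tempt a reader, and none is supported:

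- That every fatal consequence of QT prolongation misses the table. A fatal case coded to Torsade de pointes or Ventricular tachycardia is counted.
- That the list has no repolarization term. Four of its six terms describe QT prolongation or abnormality.
- That a QT-related harm is more likely to surface as a clinical event than on a tracing because scheduled ECGs are far apart. The documents give no rates for either, so the visit schedule cannot show this.

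**Conclusion.** The gap is real and narrow. Events coded to ventricular fibrillation, cardiac arrest or sudden death are not counted, listed or put forward for narrative under the ventricular-repolarization AESI. They do appear in the general TEAE output, in the SAE tables if serious and in the death output if fatal.

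The effect is on one of twelve AESI categories. No overall TEAE, SAE or death count changes, and neither does any QTcF result. If k subjects have an on-treatment event coded only to the omitted terms, a broader count would exceed the planned one by k. The documents give no event rate, so k cannot be predicted and may be 0.

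This assumes that Appendix 10 is applied exactly as written and that coding does not also assign a listed term to the same event. It is a cheap improvement to how a rare and potentially fatal kind of event is presented, and it does not challenge the study's ability to capture safety data.

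**What to change.** State in Appendix 10 how the terms were selected. Then show two tiers in the same table, each with its own count:

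- **Narrow tier:** the present six terms, unchanged.
- **Supportive broader tier:** ventricular fibrillation and flutter, ventricular arrhythmia, cardiac arrest, sudden death and sudden cardiac death. The exact Preferred Terms should be confirmed in the MedDRA version used (19.0 according to SAP Section 3.7.2), which could not be checked here.

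Extend the listing and the narrative pool to both tiers. As an option, cross-list Syncope and Loss of consciousness as a separate non-specific tier, leaving them in their present appendices as well.

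The cost is appendix wording and a programming flag, with no new data. The drawback is that the broader tier will include some events unrelated to QT, which is why its count should stay apart from the narrow one.

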Ascites Asterixis Bacterascites Biliary cirrhosis Biliary cirrhosis primary Biliary fibrosis Cholestatic liver injury Chronic hepatic failure Coma hepatic Cryptogenic cirrhosis Diabetic hepatopathy Drug-induced liver injury Duodenal varices Gastric variceal injection Gastric variceal ligation Gastric varices haemorrhage Hepatic calcification Hepatic calcification Hepatic cirrhosis Hepatic encephalopathy Hepatic encephalopathy Hepatic fibrosis Hepatic infiltration eosinophilic Hepatic infiltration eosinophilic Hepatic steatos-fibrosis Hepatic flura filary disease Hepatocellular foamy cell syndrome	Acute on chronic liver failure
Asterixis Bacterascites Biliary cirrhosis Biliary cirrhosis primary Biliary fibrosis Cholestatic liver injury Chronic hepatic failure Coma hepatic Cryptogenic cirrhosis Diabetic hepatopathy Drug-induced liver injury Duodenal varices Gallbladder varices Gallbladder varices Gastric variceal ligation Gastric variceal ligation Gastric varices haemorrhage Hepatic calcification Hepatic cirrhosis Hepatic encephalopathy Hepatic encephalopathy Hepatic encephalopathy Hepatic infiltration eosinophilic Hepatic infiltration eosinophilic Hepatic tesion Hepatic steatosis Hepatic steatosis Hepatic steatosis Hepatic steatosis Hepatic steatosis Hepatic steatosis Hepatic fibrosis Hepatic steatosis Hepatic steatosis Hepatic steatosis Hepatic steatosis Hepatic fliura disease Hepatocellular foamy cell syndrome	Acute yellow liver atrophy
Baltary cirrhosis Biliary cirrhosis primary Biliary fibrosis Cholestatic liver injury Chronic hepatic failure Coma hepatic Cryptogenic cirrhosis Diabetic hepatopathy Drug-induced liver injury Duodenal varices Gallbladder varices Gallbladder varices Gastric variceal injection Gastric variceal ligation Gastric varices haemorrhage Hepatectomy Hepatic calcification Hepatic cirrhosis Hepatic encephalopathy Hepatic influre encephalopathy Hepatic influre hepatic fibrosis Hepatic fibrosis Hepatic inflictation eosinophilic Hepatic lesion Hepatic steato-fibrosis	Ascites
Biliary cirrhosis Biliary cirrhosis primary Biliary fibrosis Cholestatic liver injury Chronic hepatic failure Coma hepatic Cryptogenic cirrhosis Diabetic hepatopathy Drug-induced liver injury Duodenal varices Gallbladder varices Gallbladder varices Gastric variceal ligation Gastric variceal ligation Gastric varices haemorrhage Hepatectomy Hepatic atrophy Hepatic calcification Hepatic cirrhosis Hepatic encephalopathy prophylaxis Hepatic fibrosis Hepatic fibrosis Hepatic infiltration eosinophilic Hepatic seato-fibrosis Hepatic seato-fibrosis Hepatic steato-fibrosis Hepatitis fulminant Hepatocellular foamy cell syndrome	Asterixis
Biliary cirrhosis primary Biliary fibrosis Cholestatic liver injury Chronic hepatic failure Coma hepatic Cryptogenic cirrhosis Diabetic hepatopathy Drug-induced liver injury Duodenal varices Gallbladder varices Gallbladder varices Gastric variceal ligation Gastric variceal ligation Gastric varices haemorrhage Hepatectomy Hepatic atrophy Hepatic calcification Hepatic cirrhosis Hepatic encephalopathy Hepatic encephalopathy Hepatic fibrosis Hepatic fibrosis Hepatic fillure Hepatic infiltration eosinophilic Hepatic steato-fibrosis	Bacterascites
Biliary fibrosis Cholestatic liver injury Chronic hepatic failure Coma hepatic Cryptogenic cirrhosis Diabetic hepatopathy Drug-induced liver injury Duodenal varices Gallbladder varices Gallbladder varices Gastric variceal injection Gastric variceal ligation Gastric varices haemorrhage Hepatic atrophy Hepatic atrophy Hepatic acloification Hepatic cirrhosis Hepatic encephalopathy prophylaxis Hepatic failure Hepatic fibrosis Hepatic hydrothorax Hepatic lesion Hepatic lesion Hepatic recrosis Hepatic necrosis Hepatic steato-fibrosis Hepatic steato-fibrosis Hepatic steato-fibrosis Hepatic steatosis Hepatic steatosis Hepatic steatosis Hepatic steatosis Hepatic fulminant Hepatocellular foamy cell syndrome	Biliary cirrhosis
Cholestatic liver injury Chronic hepatic failure Coma hepatic Cryptogenic cirrhosis Diabetic hepatopathy Drug-induced liver injury Duodenal varices Gallbladder varices Gallbladder varices Gastric variceal injection Gastric variceal ligation Gastric varices Gastric varices Gastric varices Hepatic atrophy Hepatic atrophy Hepatic aclification Hepatic cirrhosis Hepatic encephalopathy prophylaxis Hepatic failure Hepatic fibrosis Hepatic infiltration eosinophilic Hepatic necrosis Hepatic steato-fibrosis	Biliary cirrhosis primary
Chronic hepatic failure Coma hepatic Cryptogenic cirrhosis Diabetic hepatopathy Drug-induced liver injury Duodenal varices Gallbladder varices Gastric variceal injection Gastric variceal ligation Gastric varices haemorrhage Hepatic atrophy Hepatic aclification Hepatic cirrhosis Hepatic encephalopathy prophylaxis Hepatic fibrosis Hepatic filbrosis Hepatic lesion Hepatic infiltration eosinophilic Hepatic steato-fibrosis Hepatic steato-fibrosis Hepatic steatosis Hepatit steatosis Hepatitis fulminant Hepatocellular foamy cell syndrome	Biliary fibrosis
Coma hepatic Cryptogenic cirrhosis Diabetic hepatopathy Drug-induced liver injury Duodenal varices Gallbladder varices Gallbladder varices Gastric variceal injection Gastric variceal ligation Gastric varices haemorrhage Hepatectomy Hepatic atrophy Hepatic aclification Hepatic cirrhosis Hepatic encephalopathy prophylaxis Hepatic failure Hepatic fibrosis Hepatic fibrosis Hepatic infiltration eosinophilic Hepatic infiltration eosinophilic Hepatic steato-fibrosis Hepatic steato-fibrosis Hepatic steato-fibrosis Hepatic steato-fibrosis Hepatic steato-fibrosis Hepatic steatosis Hepatic steatosis Hepatic steatosis Hepatitis fulminant Hepatobiliary disease Hepatocellular foamy cell syndrome	Cholestatic liver injury
Cryptogenic cirrhosis Diabetic hepatopathy Drug-induced liver injury Duodenal varices Gallbladder varices Gastric variceal injection Gastric variceal ligation Gastric varices haemorrhage Hepatic atrophy Hepatic atrophy Hepatic calcification Hepatic cirrhosis Hepatic encephalopathy prophylaxis Hepatic failure Hepatic filorosis Hepatic infiltration eosinophilic Hepatic lesion Hepatic steato-fibrosis	Chronic hepatic failure
Diabetic hepatopathy Drug-induced liver injury Duodenal varices Gallbladder varices Gastric variceal injection Gastric variceal ligation Gastric varices Gastric varices Gastric varices Gastric varices Hepatectomy Hepatic atrophy Hepatic atrophy Hepatic calcification Hepatic cirrhosis Hepatic encephalopathy prophylaxis Hepatic failure Hepatic failure Hepatic fibrosis Hepatic infiltration eosinophilic Hepatic lession Hepatic steato-fibrosis	Coma hepatic
Drug-induced liver injury Duodenal varices Gallbladder varices Gastric variceal injection Gastric variceal ligation Gastric varices Gastric varices Gastric varices Gastric varices Gastric varices Hepatectomy Hepatic atrophy Hepatic alcification Hepatic cirrhosis Hepatic encephalopathy Hepatic encephalopathy prophylaxis Hepatic failure Hepatic fibrosis Hepatic infiltration eosinophilic Hepatic lesion Hepatic steato-fibrosis Hepatic steato-fibrosis Hepatic steato-fibrosis Hepatic steatosis Hepatit sfulminant Hepatobiliary disease Hepatocellular foamy cell syndrome	Cryptogenic cirrhosis
Duodenal varices Gallbladder varices Gastric variceal injection Gastric variceal ligation Gastric varices Gastric varices Gastric varices Gastric varices haemorrhage Hepatectomy Hepatic atrophy Hepatic calcification Hepatic cirrhosis Hepatic encephalopathy Hepatic encephalopathy prophylaxis Hepatic failure Hepatic fibrosis Hepatic infiltration eosinophilic Hepatic infiltration eosinophilic Hepatic steato-fibrosis Hepatic steato-fibrosis Hepatic steatosis Hepatit steatosis Hepatitosiliary disease Hepatocellular foamy cell syndrome	Diabetic hepatopathy
Gallbladder varices Gastric variceal injection Gastric variceal ligation Gastric varices Gastric varices Gastric varices Gastric varices haemorrhage Hepatectomy Hepatic atrophy Hepatic atrophy Hepatic calcification Hepatic cirrhosis Hepatic encephalopathy Hepatic encephalopathy prophylaxis Hepatic failure Hepatic fibrosis Hepatic fibrosis Hepatic infiltration eosinophilic Hepatic lesion Hepatic steato-fibrosis Hepatic steato-fibrosis Hepatic steatosis Hepatic steatosis Hepatic steatosis Hepatitis fulminant Hepatobiliary disease Hepatocellular foamy cell syndrome	Drug-induced liver injury
Gastric variceal ligation Gastric varices Gastric varices Gastric varices haemorrhage Hepatectomy Hepatic atrophy Hepatic calcification Hepatic cirrhosis Hepatic encephalopathy Hepatic encephalopathy prophylaxis Hepatic fibrosis Hepatic fibrosis Hepatic fibrosis Hepatic fibrosis Hepatic seasonophilic Hepatic infiltration eosinophilic Hepatic lesion Hepatic steato-fibrosis Hepatic steato-fibrosis Hepatic steato-fibrosis Hepatic steatosis Hepatic steatosis Hepatic steatosis Hepatitis fulminant Hepatobiliary disease Hepatocellular foamy cell syndrome	Duodenal varices
Gastric variceal ligation Gastric varices Gastric varices haemorrhage Hepatectomy Hepatic atrophy Hepatic calcification Hepatic cirrhosis Hepatic encephalopathy Hepatic encephalopathy prophylaxis Hepatic failure Hepatic fibrosis Hepatic infiltration eosinophilic Hepatic lesion Hepatic steato-fibrosis	Gallbladder varices
Gastric varices Gastric varices haemorrhage Hepatectomy Hepatic atrophy Hepatic calcification Hepatic cirrhosis Hepatic encephalopathy Hepatic encephalopathy prophylaxis Hepatic failure Hepatic fibrosis Hepatic hydrothorax Hepatic infiltration eosinophilic Hepatic steato-fibrosis	Gastric variceal injection
Gastric varices haemorrhage Hepatectomy Hepatic atrophy Hepatic calcification Hepatic cirrhosis Hepatic encephalopathy Hepatic failure Hepatic fibrosis Hepatic fibrosis Hepatic hydrothorax Hepatic infiltration eosinophilic Hepatic steato-fibrosis Hepatic steato-fibrosis Hepatic steato-fibrosis Hepatic steatosis Hepatic steatosis Hepatic steatosis Hepaticit fulminant Hepatocellular foamy cell syndrome	Gastric variceal ligation
Hepatic atrophy Hepatic calcification Hepatic cirrhosis Hepatic encephalopathy Hepatic failure Hepatic fibrosis Hepatic hydrothorax Hepatic infiltration eosinophilic Hepatic steato-fibrosis Hepatic steatosis Hepatic steatosis Hepatic steatosis Hepatic steatosis Hepatolliary disease Hepatocellular foamy cell syndrome	Gastric varices
Hepatic atrophy Hepatic calcification Hepatic cirrhosis Hepatic encephalopathy Hepatic encephalopathy prophylaxis Hepatic failure Hepatic fibrosis Hepatic hydrothorax Hepatic infiltration eosinophilic Hepatic lesion Hepatic steato-fibrosis Hepatic steato-fibrosis Hepatic steato-fibrosis Hepatic steatosis Hepatic steatosis Hepatobiliary disease Hepatocellular foamy cell syndrome	Gastric varices haemorrhage
Hepatic calcification Hepatic cirrhosis Hepatic encephalopathy Hepatic encephalopathy prophylaxis Hepatic failure Hepatic fibrosis Hepatic hydrothorax Hepatic infiltration eosinophilic Hepatic lesion Hepatic steato-fibrosis	Hepatectomy
Hepatic cirrhosis Hepatic encephalopathy Hepatic encephalopathy prophylaxis Hepatic failure Hepatic fibrosis Hepatic hydrothorax Hepatic infiltration eosinophilic Hepatic lesion Hepatic steato-fibrosis Hepatic steato-fibrosis Hepatic steato-fibrosis Hepatic steatosis Hepatic steatosis Hepatic fulminant Hepatobiliary disease Hepatocellular foamy cell syndrome	Hepatic atrophy
Hepatic encephalopathy Hepatic encephalopathy prophylaxis Hepatic failure Hepatic fibrosis Hepatic hydrothorax Hepatic infiltration eosinophilic Hepatic lesion Hepatic necrosis Hepatic steato-fibrosis Hepatic steatosis Hepatic steatosis Hepatic fibrosis Hepatic steatosis Hepatic steatosis Hepatic foamy cell syndrome	Hepatic calcification
Hepatic encephalopathy prophylaxis Hepatic failure Hepatic fibrosis Hepatic hydrothorax Hepatic infiltration eosinophilic Hepatic lesion Hepatic necrosis Hepatic steato-fibrosis Hepatic steatosis Hepatic steatosis Hepatic steatosis Hepatic fulminant Hepatobiliary disease Hepatocellular foamy cell syndrome	Hepatic cirrhosis
Hepatic failure Hepatic fibrosis Hepatic hydrothorax Hepatic infiltration eosinophilic Hepatic lesion Hepatic necrosis Hepatic steato-fibrosis Hepatic steatosis Hepatic steatosis Hepatic stolminant Hepatobiliary disease Hepatocellular foamy cell syndrome	Hepatic encephalopathy
Hepatic fibrosis Hepatic hydrothorax Hepatic infiltration eosinophilic Hepatic lesion Hepatic necrosis Hepatic steato-fibrosis Hepatic steatosis Hepatic steatosis Hepatic steatosis Hepatic fibrosis Hepatic steatosis Hepatic steatosis Hepatobiliary disease Hepatocellular foamy cell syndrome	Hepatic encephalopathy prophylaxis
Hepatic hydrothorax Hepatic infiltration eosinophilic Hepatic lesion Hepatic necrosis Hepatic steato-fibrosis Hepatic steatosis Hepatic steatosis Hepatitis fulminant Hepatobiliary disease Hepatocellular foamy cell syndrome	Hepatic failure
Hepatic infiltration eosinophilic Hepatic lesion Hepatic necrosis Hepatic steato-fibrosis Hepatic steatosis Hepatic steatosis Hepatitis fulminant Hepatobiliary disease Hepatocellular foamy cell syndrome	Hepatic fibrosis
Hepatic lesion Hepatic necrosis Hepatic steato-fibrosis Hepatic steatosis Hepatitis fulminant Hepatobiliary disease Hepatocellular foamy cell syndrome	Hepatic hydrothorax
Hepatic necrosis Hepatic steato-fibrosis Hepatic steatosis Hepatitis fulminant Hepatobiliary disease Hepatocellular foamy cell syndrome	Hepatic infiltration eosinophilic
Hepatic steato-fibrosis Hepatic steatosis Hepatitis fulminant Hepatobiliary disease Hepatocellular foamy cell syndrome	Hepatic lesion
Hepatic steatosis Hepatitis fulminant Hepatobiliary disease Hepatocellular foamy cell syndrome	Hepatic necrosis
Hepatitis fulminant Hepatobiliary disease Hepatocellular foamy cell syndrome	Hepatic steato-fibrosis
Hepatobiliary disease Hepatocellular foamy cell syndrome	Hepatic steatosis
Hepatocellular foamy cell syndrome	Hepatitis fulminant
	Hepatobiliary disease
Hepatocellular injury	Hepatocellular foamy cell syndrome
	Hepatocellular injury

Preferred Term
Hepatopulmonary syndrome
Hepatorenal failure
Hepatorenal syndrome
Hepatotoxicity
Intestinal varices
Intestinal varices haemorrhage
Liver and small intestine transplant
Liver dialysis
Liver disorder
Liver injury
Liver operation
Liver transplant
Lupoid hepatic cirrhosis
Minimal hepatic encephalopathy
Mixed liver injury
Nodular regenerative hyperplasia
Non-alcoholic fatty liver
Non-alcoholic steatohepatitis
Non-cirrhotic portal hypertension
Oedema due to hepatic disease
Oesophageal varices haemorrhage
Peripancreatic varices
Portal fibrosis
Portal hypertension
Portal hypertensive enteropathy
Portal hypertensive gastropathy
Portal vein cavernous transformation
Portal vein dilatation
Portopulmonary hypertension
Renal and liver transplant
Retrograde portal vein flow
Reye's syndrome
Reynold's syndrome
Splenic varices
Splenic varices haemorrhage
Steatohepatitis
Subacute hepatic failure
Varices oesophageal
Varicose veins of abdominal wall
Anorectal varices
Anorectal varices haemorrhage
Intrahepatic portal hepatic venous fistula

Preferred Term
Peritoneovenous shunt
Portal shunt
Portal shunt procedure
Small-for-size liver syndrome
Spider naevus
Splenorenal shunt
Splenorenal shunt procedure
Spontaneous intrahepatic portosystemic venous shunt
Stomal varices

